9.1.1 Derived Efficacy Variables

If only a few item scores are missing, the total score will be calculated based on available item scores using the following formula: (total number of items in the scale) \times (sum of non-missing items divided by number of items with non-missing values). The maximum number of missing items allowed for the total scores imputation and the details of the derivation is specified below Section 9.3.1 and Section 9.4.3.

9.2 Handling of Missing Data

Missing data could occur due to various reasons, including missing visits/assessments or early withdrawal from the clinical trials. Assessments on or after any intercurrent event will be handled as specified in Section 8.0.

Missing data for the efficacy analyses will be handled using the methods described below.

9.2.1 Continuous Endpoints

For missing data of continuous efficacy endpoints for the DBP and BEP, descriptive statistics and figures is provided using the following approach:

- LOCF: Only the post-baseline total score of a parameter will be imputed. Individual item score will not be carried forward. Baseline total score will be carried forward only for the intermittent missing scores immediately after baseline. If all the post-baseline values are missing, baseline value will not be carried forward.
- OC: The OC analysis will not impute values for missing evaluations, and thus a subject who does not have an evaluation on a scheduled visit will be excluded from the OC analysis for that visit. OC will exclude values after a subject prematurely discontinues from study treatment.

9.2.2 Categorical Endpoints

For binary efficacy endpoints where logistic regression model is performed, missing data will be handled using the LOCF approach, the OC approach and the following approaches:

- Non-Responder Imputation (NRI): the NRI method will categorize any subject who does not have evaluation during a specific visit window as a non-responder for that visit.

The LOCF and OC approaches used for categorical efficacy endpoints are defined as the same method as for continuous efficacy endpoints.

Response for each subject will be derived based on the imputed score.

9.3 Primary Efficacy Endpoint and Analyses

9.3.1 Primary Efficacy Endpoint

The primary endpoint for the primary analysis of efficacy is:

- Change in SCI-PANSS total score from baseline to DBP Week 6.

The SCI-PANSS total score will be derived as the sum of the 30 items (P1-P7, N1-N7, and G1-G16) of SCI-PANSS, using this formula: (total number of items in the scale) \times (sum of non-missing items divided by number of items with non-missing values). If more than 3 items for the SCI-PANSS total score are missing, the total score will be set to missing.

9.3.2 Main Analysis of Primary Efficacy Endpoint

Analysis of the primary endpoint will be conducted on the mITT based on treatment as randomized. Descriptive statistics and figures including mean difference between cariprazine group and placebo group from baseline to Week 6 will be provided using the LOCF approach or the OC approach by treatment group and by time point, respectively. Details on the analysis, output are specified in Section 9.1 and Section 9.2.1.

The attributes of the estimand corresponding to the primary efficacy objective are summarized in Table 1.

Table 1. Summary of the Estimand Attributes Corresponding to the Primary Efficacy Objective

Attributes of the Estimand					
Estimand Label	Treatment	Endpoint	Population	Handling of Intercurrent Events	Statistical Summary
Primary	Cariprazine 6 mg/day vs. placebo	Change from baseline to Week 6 of the DBP in SCI-PANSS total score.	mITT (all randomized subjects who receive at least 1 dose of study drug and have both baseline and at least 1 postbaseline value of SCI-PANSS total score during the DBP)	Regardless of whether rescue medications are used, data are included in the analysis. Data after discontinuation of study drug will not be included in the primary analysis and will be assumed missing at random.	Difference in means between cariprazine 6 mg/day group and placebo

9.4 Secondary Efficacy Endpoints and Analyses

9.4.1 Key Secondary Efficacy Endpoint for DBP

The key secondary endpoint of efficacy is:

- Change in Clinical Global Impression-Severity (CGI-S) score from baseline to Week 6

9.4.2 Main Analyses of Key Secondary Efficacy Endpoint for DBP

Analysis of key secondary endpoint will be conducted on the mITT based on treatment as randomized. Similar to the primary endpoint, descriptive statistics and figures including mean difference between cariprazine group and placebo group from baseline to Week 6 will be provided using the LOCF approach or the OC approach by treatment group and by time point, respectively.

The attributes of the estimand corresponding to the key secondary efficacy objective are summarized in Table 2.

Table 2. Summary of the Estimand Attributes Corresponding to the Key Secondary Efficacy Objective

Attributes of the Estimand					
Estimand Label	Treatment	Endpoint	Population	Handling of Intercurrent Events	Statistical Summary
Key secondary	Cariprazine 6 mg/day vs. placebo	Change from baseline to Week 6 of the DBP in CGI-S score.	mITT (all randomized subjects who receive at least 1 dose of study drug and have both baseline and at least 1 postbaseline value of SCI-PANSS total score during the DBP)	Regardless of whether rescue medications are used, data are included in the analysis. Data after discontinuation of study drug will not be included in the primary analysis and will be assumed missing at random.	Difference in means between cariprazine 6 mg/day group and placebo

9.4.3 Additional Secondary Efficacy Endpoints for DBP and Analyses

The additional secondary efficacy endpoints for DBP are:

- Change in SCI-PANSS positive symptom score from baseline to Week 6
- Change in 16-Item Negative Symptom Assessment (NSA-16) total score to baseline to Week 6
- Change in SCI-PANSS negative symptom score from baseline to Week 6
- Change in SCI-PANSS negative factor score from baseline to Week 6

The below scores are derived using this formula: (total number of items in the scale) × (sum of non-missing items divided by number of items with non-missing values).

- The PANSS positive symptom score is the sum of the 7 positive items (P1-P7) of PANSS. If any item for the PANSS positive score is missing, the positive score will be set to missing.

- The NSA-16 total score is the sum of the 16 items of the NSA. If more than 2 items for the NSA-16 total score are missing, the total score will be set to missing.
- The PANSS negative symptom score is the sum of the 7 negative items (N1-N7) of PANSS. If any item for the PANSS negative score is missing, the negative score will be set to missing.
- The PANSS negative factor score was developed by Marder, et al (Marder et al, 1997) and is the sum of the 7 items (N1, N2, N3, N4, N6, G7 and G16) of PANSS. If any item for the PANSS negative factor score is missing, the negative factor score will be set to missing. Negative factor score ranges from 7-49.

For the above mentioned continuous endpoints, descriptive statistics including mean difference between cariprazine group and placebo group from baseline to Week 6 will be provided using the LOCF approach or the OC approach by treatment group and by time point, respectively. Details of the analysis and output are specified in Section 9.1 and Section 9.2.1.

9.4.4 Additional Efficacy Endpoints and Analyses

The additional efficacy endpoints for DBP are:

- PANSS responder (subjects with SCI-PANSS total score improved by $\geq 30\%$ at Week 6 compared with Baseline)

For the PANSS responder, the number, percent and 2-sided 95% CI will be provided using the LOCF approach, the OC approach or the NRI approach, respectively. Details on the analysis, output are specified in Section 9.1 and Section 9.2.2.

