Cariprazine 6 mg/day	1.5 mg	3 mg	4.5 mg	6 mg

18-Week Blinded Extension Period

Subjects who completed the 6-week DBP are likely to comply with the study protocol and are suitable for participation in BEP as judged by the investigator (or subinvestigator) are eligible to participate in the 18-week BEP of this study.

Subjects in the cariprazine 6 mg/day dosing group in the DBP will receive cariprazine 3 mg/day, and subjects from the placebo group in DBP will receive cariprazine 1.5 mg/day in a blinded manner at Week 6 (Visit 8) after completion of scheduled study activities.

At Weeks 8, 12, 16, and 20, the dose can be increased in 1 step (1.5 mg/day to 3 mg/day or 3 mg/day to 6 mg/day) if the subject meets either of the following dose-escalation criteria after treatment of 2 weeks (Week 8) or at least 4 weeks (Weeks 12, 16, and 20) with stable dose and with no tolerability problem judged by the investigator (or subinvestigator) (optional dose escalation):

- Improvement in SCI-PANSS total score from Day 1 (Visit 2) is < 20% and CGI-S score is ≥ 4
- The investigator's (or subinvestigator's) judgment

The maximum dose of cariprazine is 6 mg/day.

An interruption in dosing of up to 3 days is allowed at any time if the investigator (or subinvestigator) has judged that there is a tolerability problem.

Subjects with a tolerability problem or well-maintained subjects judged by the investigator (or subinvestigator) can reduce the dose by 1 step (6 mg/day to 3 mg/day or 3 mg/day to 1.5 mg/day) in a blinded manner at any visit, including unscheduled visits.

Safety Follow-Up Period

Subjects will enter the 8-week safety follow-up period after the last dose of study drug in the study (either DBP or BEP).

Switching to Another Antipsychotic After Completion of Study Treatment

In switching to another antipsychotic after completion of study treatment, the use of antipsychotics should be limited to only 1 atypical antipsychotic, and the dose should be increased according to

symptoms after at least 1 week of treatment with the antipsychotic agent at the initial dose recommended.

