 - Subjects diagnosed with schizophrenia according to the diagnostic criteria of the Diagnostic Statistical Manual of Mental Disorders, Fifth Edition, Text Revision (DSM-5), and Mini International Neuropsychiatric Interview (MINI).
- ✓ 10. A history within 2 months before informed consent of a psychotic episode (evidence of schizophrenia exacerbation) requiring treatment modifications (hospitalization or a change or dose increase of antipsychotic drugs) as judged by the investigator (or subinvestigator). The following must be met at the time of the screening visit (Visit 1):
 - Persistence of the psychotic episode stated above
 - SCI-PANSS total score ≥ 80 and ≤ 120
 - At least 2 of the 4 SCI-PANSS positive symptoms (P1. delusions, P2. conceptual disorganization, P3. hallucinatory behavior, and P6. suspiciousness/persecution) rated as 4 (moderate) or higher
 - CGI-S score ≥ 4
 - Physical examination findings, vital signs, clinical laboratory test results, and ECG results that are normal; or some of the results are abnormal but not clinically significant as judged by the investigator (or subinvestigator) and documented as such in the source documents
 - Subjects must agree to start hospitalization for washout of all psychotropics and lemborexant except rescue medications during screening until Week 2 of the treatment period (Visit 4; see [Figure 2](#))
- ✓ 11. Subject meets the SCI-PANSS and CGI-S criteria above in Criterion #10 at baseline (Visit 2).

Subject History

- ✓ 12. Subjects who do NOT meet any of the following criteria at the time of informed consent:
 - Hospitalization continuing for 3 months or more (except hospitalization for social reasons)
 - Patients during involuntary hospitalization by law except patients who understand clinical study procedures and are willing to follow protocol stipulations
- ✓ 13. No current diagnosis of any of the following conditions according to the diagnostic criteria of the DSM-5:
 - Schizoaffective disorder, schizophreniform disorder, and other psychotic disorders within schizophrenia spectrum
 - Bipolar I or II disorder
 - Impaired intellectual ability, mild or major neurocognitive disorder, delirium, and other cognitive disorders
 - Known or suspected borderline or antisocial personality disorder or other personality disorder of sufficient severity to interfere with participation in this study
 - Substance-related disorder (other than tobacco or caffeine) within 6 months before Visit 1 (screening visit)

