2.4 Sample Size Determination

In terms of the change from baseline in the SCI-PANSS total score at Week 6, the sample size of 125 subjects per arm (N = 250) can achieve at least 90% power at overall 0.05 two-sided significant level to detect the statistically significant difference between placebo and cariprazine 6 mg/day based on these assumptions using a Mixed-Effect Model for Repeated Measurement (MMRM); treatment difference of -8.3 between 6 mg/day and placebo based on the full analysis set (FAS) 2 in Studies A002-A4 and RGH-MD-04, and common standard deviation of 20 at Week 6 taking into account dropout rates and correlation matrix based on FAS in Study A002-A4.

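### Does the 30% PANSS responder definition need a stated percent formula, or a correction for the scale minimum of 30?

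*SAP*

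**What the plan says.** SAP 9.4.4 lists one additional efficacy endpoint for the double-blind period: "PANSS responder (subjects with SCI-PANSS total score improved by" at least 30% at Week 6 compared with baseline. It is reported as number, percent and 95% confidence interval under LOCF, OC and non-responder imputation. For detail it points to SAP 9.1 and 9.2.2. SAP 9.2.2 adds "Response for each subject will be derived based on the imputed score". None of these sections writes out a percent formula.

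The parts of the calculation are defined elsewhere:

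- **Score.** SAP 9.3.1: "The SCI-PANSS total score will be derived as the sum of the 30 items", with proration when up to 3 items are missing.
- **Baseline.** SAP 7.1 takes the Visit 2 value for efficacy variables.
- **Baseline range.** Protocol 5.1, criterion 10, requires "SCI-PANSS total score ≥ 80 and ≤ 120" at screening. Criterion 11 carries this forward: "Subject meets the SCI-PANSS and CGI-S criteria above in Criterion #10 at baseline (Visit 2").
- **Item range.** SAP 9.4.3 says of a 7-item PANSS sum: "Negative factor score ranges from 7-49".

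Protocol 4.1 also uses a percentage improvement of the same score against the same visit without a formula: "Improvement in SCI-PANSS total score from Day 1 (Visit 2) is < 20"%.

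**The concern.** A percentage of a score is easiest to interpret when zero means no symptoms. The PANSS total has no such zero, because every item scores at least 1. A subject who starts at 80 and loses every symptom ends at 30, a fall of 50/80 = 62.5% on the raw scale. One can therefore calculate the percentage from the raw baseline or from the baseline minus 30, and the two calculations classify some subjects differently. The SAP writes formulas for simpler quantities, such as treatment duration, compliance and disease duration, so the lack of one here stands out.

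If the definition really were open, a reader of the report could not tell which response rate was shown, and the choice could be made after the data were seen.

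**Working it through.** **Inputs.** Cut-off 30% (SAP 9.4.4). 30 items (SAP 9.3.1). Item range 7/7 = 1 to 49/7 = 7 (from SAP 9.4.3), so the total runs from 30 to 210. Baseline b from 80 to 120 (Protocol 5.1, criteria 10 and 11). "common standard deviation of 20 at Week 6" and a treatment difference of 8.3 (SAP 2.4). 34 subjects randomized (SAP 1.0). The plan states no point threshold for response, so there is no figure of its own to reproduce.

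**Step 1: the two rules.** Raw rule: 100 × (b − Week 6)/b ≥ 30, which needs a fall of 0.3b. Floor-corrected rule: 100 × (b − Week 6)/(b − 30) ≥ 30, which needs 0.3(b − 30) = 0.3b − 9.

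| b | raw fall | attainable, b − 30 | raw fall / attainable | corrected fall | corrected fall / b |
|---|---|---|---|---|---|
| 80 | 24 | 50 | 48.0% | 15 | 18.8% |
| 100 | 30 | 70 | 42.9% | 21 | 21.0% |
| 120 | 36 | 90 | 40.0% | 27 | 22.5% |

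The arithmetic behind the concern is right. Everyone who responds under the raw rule also responds under the corrected one, so the raw rate can only be equal or lower.

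**Step 2: which rule does the text state?** The definition names one score, one reference value (Visit 2) and one comparison (Week 6 against that value). Those three elements give (b − Week 6)/b and nothing else. The corrected rule needs a further quantity, the scale minimum, as something to subtract. Neither document states a minimum for the total or subtracts one anywhere; the 30 has to be inferred from the range of a different score. There are therefore not two readings of the text. There is one reading and one alternative endpoint.

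**Step 3: is the stated rule too strict?** The 40% to 48% figures express the threshold as a share of attainable improvement. The SAP does not define response that way, so they describe the rule without contradicting it. A stricter cut-off is not an error.

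**Step 4: what would the alternative change?** Take changes as normal with SD 20 and let Φ be the standard normal distribution function. With mean change m, the response rate is Φ((−cut-off − m)/20).

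- *Rate within an arm.* For b = 100, m = −20: raw Φ(−0.50) = 30.9%, corrected Φ(−0.05) = 48.0%. Over b = 80 to 120 and assumed m = −5 to −30, the corrected rate is higher by 7.5 to 17.8 percentage points. If the distribution is truncated to 30–210, the range is 7.5 to 19.2. Any easier threshold would raise the rate in the same way.
- *Contrast between arms.* For b = 100, placebo m = −15 and cariprazine m = −15 − 8.3 = −23.3: raw 36.9% − 22.7% = 14.2 points, corrected 54.6% − 38.2% = 16.4 points, a shift of +2.2. Over the same baselines and assumed placebo means of −5 to −25, the shift runs from −3.1 (b = 80, m = −25) to +4.4 (b = 110, m = −5). With an assumed 17 subjects in an arm, 17 × 0.044 = 0.7 of a subject.

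**The case for a change.** The strongest case for the concern is that here the reported percentage is itself the result. With no test planned, what readers take away is the response rate in each arm, and the two rules could differ by 7.5 to 17.8 percentage points within an arm. At an assumed 11 to 17 subjects per arm, that is 11 × 0.075 = 0.8 to 17 × 0.178 = 3.0 responders. A printed formula would cost one line, and SAP version 3.0 was written after early termination, when precision about definitions matters most.

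Part of this stands. No formula is printed, the raw scale has no true zero, and writing the formula out would be harmless. It would also change no result, because it would restate the rule the words already give. The 1 to 3 responders measure the distance to a rule that the plan does not contain, so they do not measure uncertainty about the rule it does contain. The count is also only illustrative: the SAP gives no arm sizes, and because the 3 mg/day subjects are included in the double-blind analyses, some arms may be smaller than 11 and the pooled cariprazine group larger than 17.

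The wish to show a floor-corrected rate beside the stated one is a methodological preference. It would add a second responder endpoint, under three missing-data approaches, after termination. Nothing in the documents calls for it.

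**Conclusion.** There is no defect. The responder definition is determinate: the fall from the Visit 2 total to the Week 6 total, divided by the Visit 2 total, at least 30%. That this takes 24 to 36 points, or 48% down to 40% of the attainable improvement, is a property of the chosen cut-off. It is neither a miscalculation nor a contradiction.

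The stakes are small as well. The endpoint is additional in SAP 9.4.4 and is not among the endpoints in Protocol 3.3. SAP 9.1 and 12.0 rule out tests and type I error control, and the primary endpoint is an absolute change that no percent formula touches. Changing the rule would move the treatment contrast by −3.1 to +4.4 percentage points, with either sign.

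These sizes rest on normal changes, the SAP's SD of 20 and difference of 8.3, assumed mean changes, baselines within 80 to 120, and at most 17 subjects in an arm for the statement in subjects. The conclusion that the definition is clear rests on the wording alone and needs none of them. The Statistical Programming Plan is not among the documents. SAP 9.4.4 does not refer to it, and the conclusion does not depend on it.

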9.4.5 Efficacy Endpoints for BEP and Analyses

The efficacy endpoints for BEP are:

- Change in SCI-PANSS total score from baseline and Week 6 to Week 24

- Change in CGI-S score from baseline and Week 6 to Week 24
- Change in SCI-PANSS positive score from baseline and Week 6 to Week 24
- Change in NSA-16 total score from baseline and Week 6 to Week 24
- Change in SCI-PANSS negative symptom score from baseline and Week 6 to Week 24
- Change in SCI-PANSS negative factor score from baseline and Week 6 to Week 24

Descriptive statistics and figures from baseline to Week 24, and from Week 6 to Week 24 will also be provided using the LOCF approach or the OC approach by modal daily dose and by time point, respectively. Details on the analysis, output are specified in Section 9.1 and Section 9.2.1. Subjects will be grouped according to their modal (most frequent) daily dose during the BEP.

9.5 Efficacy Subgroup Analyses

To evaluate the consistency of the efficacy over demographic and other specific baseline characteristics, subgroup analysis will be performed using the descriptive statistics for the primary endpoints for the subgroups below.

For subgroup analysis, descriptive statistics for each treatment group as well as mean and its 95% CI for treatment differences between cariprazine group and placebo group will be presented using the LOCF approach or the OC approach. No p-value will be provided.

- Age category (< 40 years or \geq 40 years)
- Sex (Male or Female)
- Region (Japan or Taiwan)
- SCI-PANSS total score at Baseline (<100 or \geq 100)
- Negative symptom at Baseline (Applicable or Not applicable)
 - The patients with SCI-PANSS negative factor score \geq 24 and the score of at least two items out of three items for N1, N4, and N6 \geq 4 at Screening or Day 1 will be regarded as “Applicable”.

For each subgroup for SCI-PANSS total score and Negative symptom, if there are no applicable subjects for any category, its subgroup analysis will not be performed.

10.0 Safety Analyses

10.1 General Considerations

Safety data during the DBP and BEP will be summarized for the safety population and BEP population, respectively. Safety summaries during the DBP and BEP will be presented by treatment group (modal daily dose for BEP), including a total group for all subjects on active study treatment, respectively.

Safety data during the Safety Follow-up Period will be summarized for the safety population. The double-blind treatment subjects actually received during the DBP and modal daily dose during the BEP correspond to the treatment groups that will be used for summaries of safety data during the Safety Follow-up Period for subjects who did not enter the BEP and subjects who entered the BEP, respectively. The Safety Follow-up Period starts the day after the last dose of study drug in the study (either during the DBP or BEP).

Unless otherwise specified, safety data will be summarized by period.

For all safety endpoints, the data from subjects who were randomized to cariprazine 3 mg/day prior to removal of this dose arm from the DBP will be included in analyses of the DBP.

